The objective of this randomized controlled trial is to investigate if motivational interviewing provided as an add-on intervention to a physical activity intervention will increase the average daily step count in community-dwelling participants above the age of 70.

1. It is hypothesized that motivational interviewing, will enhance the average daily step count among participants.
2. It is hypothesized that motivational interviewing, will affect self-reported physical activity and quality of life.
3. It is hypothesized that self-efficacy and outcome expectancy for exercise, will mediate the effect and explain heterogeneity in the results.

8. Trial design

Study Type: Interventional

Estimated Enrollment: 154 participants

Allocation: Randomized

Intervention Model: Parallel Assignment

12-week intervention with two groups in a parallel design

Masking: Double (Investigator, Outcomes Assessor)

Primary investigator will be blinded for allocation before making the final analyses. No outcome assessments will be made by an assessor. Only objectively measured steps per day and participant reported outcome measures will be used for this study.

Primary Purpose: Prevention

The primary hypothesis will be investigated with a superiority analysis.

Methods: Participants, interventions, and outcomes

9. Study setting

Description of study settings (e.g., community clinic, academic hospital) and list of countries where data will be collected. Reference to where list of study sites can be obtained'.

This RCT will be conducted in Denmark. Participants eligible for inclusion will receive the content necessary for participation by mail. The participants will only have contact with the research team via phone or e-mail correspondence.

10. Eligibility criteria

Participants will be considered eligible for inclusion if they; 1) are retired and community-dwelling, 2) at least 70 years of age by the day of enrolling the trial, 3) own a smartphone or tablet able to install the *Garmin Connect application*, 4) have an email address and are able to correspond and complete the study survey on a computer and 5) have hearing abilities sufficient to receive a telephone interview.

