	
guide is compiled that enabled the counselor to refer participants to specific community resources (e.g., walking groups).
 
In addition to the telephone based motivational interviews, the experimental group will also receive the "base intervention" which is described in detail under the "control intervention paragraph".
 
Behavioral: Base intervention
 
The "base intervention" consists of a physical activity monitor (PAM) for everyday use in the intervention period and a pamphlet with information about Danish recommendations on physical activity in aging populations. The PAM will be the Garmin Vivofit 3 monitor linked to a pre-specified Garmin Connect account. The participants will be asked to install the Garmin Connect application on their smartphone and use the given ID/password in the app. The participants will be asked to wear the monitor 24-hours a day for the 12-week intervention period. The participants can use the PAM as they like but they will be asked to try to use the PAM and the application to enhance their daily level of physical activity.

Active Comparator: Control intervention
 
Base intervention
	
Behavioral: Base intervention
 
The "base intervention" consists of a physical activity monitor (PAM) for everyday use in the intervention period and a pamphlet with information about Danish recommendations on physical activity in aging populations.
 
The PAM will be the Garmin Vivofit 3 monitor linked to a pre-specified Garmin Connect account. The participants will be asked to install the Garmin Connect application on their smartphone and use the given ID/password in the app. The participants will be asked to wear the monitor 24-hours a day for the 12-week intervention period. The participants can use the PAM as they like but they will be asked to try to

	use the PAM and the application to enhance their daily level of physical activity.
--	--

11.b, Fidelity

The intervention (and the actual content of the motivational interviews) will be tailored to the individual participant, but the number of calls will not be adjusted.

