The project telephone counselor has a masters degree in physiotherapy and additional training in the MI approach to telephone health behavior counseling. Training involved a four-day course, reading study materials, discussions with previous study investigators, viewing of MI recording, and roll plays. Prior to this study the counselor has also conducted more than 200 interviews with older adults and staff in the community to familiarize with the community culture and local resources.

During the study, with participants' verbal consent, telephone MI (and control) sessions is audiotaped on a regular basis to ensure fidelity of intervention delivery and to provide counselor feedback. Based on a review of these recordings the fidelity monitoring is conducted by two experienced independent MI coders who are blinded to treatment assignment using the Motivational Interviewing Treatment Integrity (MITI) Scale, a tool developed to measure MI treatment adherence [30].

12. Outcomes

Primary Outcome Measure:

1. Individual intervention period average steps per day, recorded every day by the PAM. The average number of steps per day throughout the 12 weeks will be the primary outcome for the individual participant.

Time frame: A daily average of the 12 weeks of intervention

The Garmin Vivofit 3 will serve as the PAM and thus, measure the primary outcome. Garmin Vivofit 3 has to our knowledge only been validated in older adults by our own research group (manuscript being prepared for submission).

Four physical activity monitors were included in the validation study; Misfit Shine, Nokia GO, Jawbone UP and Garmin Vivofit 3. The aim of the study was to compare different PAMs on different body locations. All hip-worn PAMs fulfilled the a priori hypothesized moderate criterion validity, when evaluating all participants. The hip-worn Garmin Vivofit 3 fulfilled the a priori

hypothesized criterion validity evaluating all participants, participants with rollator and participants without rollators and it was evaluated as the best performing device in older adults in general.

The validation study is currently being finalized for submission.

Secondary Outcome Measures:

1. International Physical Activity Questionnaire [Time Frame: Baseline + end point at 12 weeks + follow up at 6 months and 12 months]
2. Nordic Physical Activity Questionnaire [Time Frame: Baseline + end point at 12 weeks + follow up at 6 months and 12 months]

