3. EQ5D Quality of life questionnaire [Time Frame: Baseline + end point at 12 weeks + follow up at 6 months and 12 months]
4. UCLA Loneliness Scale [Time Frame: Baseline + end point at 12 weeks + follow up at 6 months and 12 months]
5. Self-Efficacy for Exercise [Time Frame: Baseline + end point at 12 weeks + follow up at 6 months and 12 months]
6. Outcome expectancy for Exercise-2 [Time Frame: Baseline + end point at 12 weeks + follow up at 6 months and 12 months]
7. Copenhagen Social Relations Questionnaire [Time Frame: Baseline + end point at 12 weeks + follow up at 6 months and 12 months]

Secondary outcome measures include participant reported outcomes administered by online questionnaires. The baseline measurement will be undertaken before the intervention group receives the first motivational interview and the end point measurement will be undertaken in the days after the last motivational interview.

International Physical Activity Questionnaire short form (IPAQ-SF)

The seven-item IPAQ-SF measure assesses the types of intensity of physical activity and sitting time that people has done the past seven days as part of their daily lives are considered to estimate total physical activity in MET-min/week and time spent sitting [31]. The score is categorized to three levels of (categories) of PA; low, moderate and high [32]. In a review of 16 international studies of

the measurement properties IPAQ-SF showed acceptable reliability (Spearman's rho: 0,32-0,88) [31] and low to moderate concurrent validity against accelerometer had a pooled correlation coefficient of 0.30 (Spearman's rho range: 0,09-0,38) [33]. The Danish version have been used in a Danish population of older adults [34].

Nordic Physical Activity Questionnaire short (NPAQ-short)

The two-item NPAQ-short [35] is a short revised version of the original NPAQ, a survey tool based on telephone interviews designed for assessment of Moderate and Vigorous Physical Activity (MVPA). It is developed to monitor compliance with the WHO recommendations on PA [36] and has showed moderate correlation with objectively measured MVPA (Spearman's rho: 0.33) in a Danish population with an average age of 43 (range: 17-85) [35].

The 5-level EuroQol-5 Domain (EQ-5D-5L) Quality of life questionnaire

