Participants will be randomized using STATA, which is a statistical software package. Allocation concealment will be ensured, as the allocation will not be available until the patient has been recruited into the trial, which takes place after the baseline step count measurements have been completed.

16.c Implementation

One investigator will be in charge of the randomization. That investigator will receive a list of participant IDs every week and randomize the participants according to the above. That one investigator will not have anything do to with recruitment nor statistical analyses.

17. Blinding (masking)

17. a

Outcome assessors and data-analysts will be blinded for participant allocation.

17b.

Due to the nature of the intervention neither participants nor staff conducting the motivational interview in the intervention group can be blinded to allocation but are strongly inculcated not to disclose the allocation status of the participants with the principal investigator who will conduct the analyses. The group names of the intervention and the control group will be anonymized before the data will be analyzed to ensure blinding of the principal investigator.

Methods: Data collection, management, and analysis

18. Data collection methods

18a. Plans for assessment and collection of outcomes

Primary outcome

The primary outcome (average steps per day in the 12-week intervention period) will be extracted from the data management software Fitrockr. Participants will be asked to synchronize their PAMs and their Garmin Connect application daily, ensuring daily storage of the step counts. The PAMs have a 30-day storage for daily totals so data will not be lost, even if the participants forget to synchronize their PAMs for longer periods of time. Fitrockr will extract the data from Garmin Connect and make daily step counts available for export through their service. When the participant has completed the 12-week intervention, the daily totals will be extracted as 84 variables (12*7). After the data extraction, the average daily step count will be calculated.

Secondary outcomes

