The secondary outcomes are all participant reported and administered through SurveyXact. All participants will receive an email with an electronic SurveyXact invitation on the day of randomization. On the last day of intervention (day 84), the participants will receive a similar SurveyXact invitation with the end-point questionnaire. The six and 12-month follow up assessments will be administered in similar ways to the end-point assessment.

Demographic and other baseline items

Non-outcome variables will be included in the baseline questionnaire.

18b. Plans to promote participant retention and complete follow-up.

If possible, reasons for drop out will be collected from each discontinued participant. The available data on the primary outcome will be used to calculate the intervention period average steps per day. If the participant fails to synchronize the PAM and a possible drop out is suspected, a person from the research team will call the participant to either remind them to synchronize the PAM or try to motivate the participant to continue the intervention.

Lost to follow up with the end-point or follow up questionnaires will be reminded via email 7, 14 and 21 days after the deadline.

19. Data management

All outcomes will be handled and stored electronically.

Steps per day will be stored every time the participant synchronizes the PAM. The data handling responsible Fitrockr will extract data from the Garmin applications and store it according to the agreements. Every time a participant completes the intervention period, their data will be exported from the Fitrockr database and stored securely at the University of Copenhagen server.

During the study, with participants' verbal consent, telephone MI (and control) sessions is audiotaped on a regular basis to ensure fidelity of intervention delivery and to provide counselor feedback.

The participant reported outcomes for the secondary outcomes will be administered using SurveyXact, securing data every time a survey has been completed. Every time a participant completes the intervention period, their data will be exported from the Fitrockr database and stored securely at the University of Copenhagen server.

No personal data will be exported from Fitrockr or SurveyXact without pseudonymization. Complete anonymization of all data will be done after the last follow up period. Data protection agency approval Reference number: 514-0268/18-3000

20. Statistical methods

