The primary outcome will be analyzed as a mixed effects model, where intervention group are analyzed fixed and participants are random effects. The analysis will investigate the group difference in average daily step count, adjusted for baseline step count and gender. Same analysis will be performed on secondary outcomes.

Drop outs with data on the primary outcome for at least one week will have their average daily step count based on the available days. All analysis will be performed following the Intention to Treat (ITT) principle imputing missing data using a multiple imputation based on age, gender, baseline step counts and average daily step count (for missing data on the secondary outcomes). In

calculating the average daily step count, days with less than 100 steps will be handled as “days of non-wear” and excluded assessing the mean step count.

Methods: Monitoring

21. Data monitoring

Not applicable/relevant

22. Harms

In our study an adverse event will be defined as any untoward medical occurrence in a participant without regard to the possibility of a causal relationship with the intervention. Adverse events will be collected after the subject has provided consent and enrolled in the study. If a participant experiences an adverse event after the electronically administered informed consent has been signed (entry) but the subject has not started to receive study intervention, the event will be reported as not related to the intervention. All adverse events occurring after entry into the study will be recorded. The participants will be asked at the end-point questionnaire if they experienced any adverse events in terms of using the PAMs or trying to enhance their daily amount of physical activity.

23. Auditing

No auditing has been protocolled.

Ethics and dissemination

24. Research ethics approval

According to a written correspondence with the Danish Ethics Committee in the Capital Region of Denmark, this trial was not subject to the current laws on research ethics in Denmark due to the non-invasive behavioral change intervention. The study can be conducted without further approval from the Danish Ethics Committee in the Capital Region of Denmark (Journal-nr.:18004960).

25. Protocol amendments

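### Mediation of the 12-week step effect cannot be tested, because self-efficacy and outcome expectancy are first re-measured on or after the last day of the step window

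*Combined protocol and SAP*

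**What the plan says.** Section 7 lists three hypotheses. The third is that "self-efficacy and outcome expectancy for exercise, will mediate the effect and explain heterogeneity in the results". The objective and Hypothesis 1 concern average daily steps; Hypothesis 2 concerns self-reported activity and quality of life.

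Section 12 defines the step outcome: "The average number of steps per day throughout the 12 weeks will be the primary outcome for the individual participant", with time frame "A daily average of the 12 weeks of intervention". Section 18a extracts it as 84 daily totals. Section 11 limits wear to the same period: "The participants will be asked to wear the monitor 24-hours a day for the 12-week intervention period".

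Section 12 schedules SEE-DK (self-efficacy) and OEE2-DK (outcome expectancy) at baseline, at 12 weeks, and at 6 and 12 months of follow-up. Of the 12-week measurement it says that "the end point measurement will be undertaken in the days after the last motivational interview". Section 18a gives the day: "On the last day of intervention (day 84), the participants will receive a similar SurveyXact invitation with the end-point questionnaire". Section 18b adds reminders 7, 14 and 21 days after the deadline.

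Section 20 specifies a group comparison of steps adjusted for baseline steps and gender, then adds: "Same analysis will be performed on secondary outcomes". It contains no mediation model and no interaction between group and a baseline score.

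**The concern.** A mediator has to change before the outcome that it is said to carry. Here the whole step outcome has in effect accrued before either proposed mediator is measured again. Someone who has walked more for twelve weeks may well report more confidence about exercise at the end. That would link group, steps and the day-84 score just as mediation would.

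The mechanism is one of three stated hypotheses, and Section 11 presents motivational interviewing as working through self-efficacy. A mediation analysis of the step average is therefore likely to be attempted and read causally. The primary group comparison of steps is not affected.

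**Working it through.** **The plan's own figure.** Section 14 gives 128 participants for a 0.5 SD difference at 80% power and a 0.05 level. A two-sided two-sample t-test needs 63.77 per arm, so 64 per arm and 128 in total. Adding 20% gives 128 × 1.2 = 153.6, so 154. Both figures reproduce. They size the primary comparison and were not derived for Hypothesis 3.

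**Order in time.**
- Step outcome: days 1 to 84 (Sections 12 and 18a).
- Interview calls: weeks 1, 2, 3, 5, 7, 9 and 12 (Section 11).
- First post-baseline SEE-DK and OEE2-DK: requested on day 84, completed then or later (Sections 18a and 18b).
- Step days accrued by then: at least 84 − 1 = 83.
- Mediator measurements on days 1 to 83 of the intervention: none. Step data planned after day 84: none.
- Self-reported activity (IPAQ, NPAQ) at 6 and 12 months: after the day-84 scores.

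No post-randomisation mediator value precedes the step outcome. One does precede the later self-reported outcomes.

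**How often the reverse path would pass for mediation.** The effect sizes here are assumptions, except the 0.5 SD from Section 14. Take 64 per arm, a 0.5 SD group effect on steps, no effect of mediator on steps, and day-84 score = c × steps + noise, scaled to unit variance within arm. Then:
- group to mediator: a = 0.5c, SE = 2/√128 = 0.177;
- mediator to steps given group: b = c, with test statistic about c√125/√(1 − c²);
- apparent share mediated: ab/0.5 = c²;
- chance of significance for a statistic centred at z: Φ(z − 1.96) + Φ(−z − 1.96).

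| c | z for a | P(a significant) | z for b | P(b significant) | Product | Simulated | Apparent share |
|---|---|---|---|---|---|---|---|
| 0.2 | 0.57 | 0.087 | 2.28 | 0.63 | 5% | 5.2% | 4% |
| 0.3 | 0.85 | 0.136 | 3.52 | 0.94 | 13% | 13.1% | 9% |
| 0.4 | 1.13 | 0.205 | 4.88 | 1.00 | 20% | 19.8% | 16% |
| 0.5 | 1.41 | 0.293 | 6.45 | 1.00 | 29% | 29.6% | 25% |

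The simulation used 4,000 replicates per setting. With 154 participants the rates are about 7%, 15%, 22% and 34%.

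**Heterogeneity by baseline score.** For an assumed interaction of 0.25 SD of steps per SD of baseline score and 128 participants, SE = 0.177 × √(1 − ρ²), where ρ is the correlation of baseline with 12-week steps. The documents do not give ρ.
- No baseline-step adjustment: 0.25/0.177 = 1.41, power 29%.
- ρ = 0.5: 0.25/0.153 = 1.63, power 37%.
- ρ = 0.7: 0.25/0.126 = 1.98, power 51%.
- ρ = 0.8: 0.25/0.106 = 2.36, power 65%.

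**Mediation of later activity needs the step average in the model.** Steps on days 1 to 84 can raise both the day-84 score and later activity. Assume both paths are 0.5, the mediator has no effect, and baseline activity correlates 0.5 with 12-week steps. Given group and baseline, the residual step variance is 1 − 0.25 = 0.75. The score and later activity then have covariance 0.5 × 0.5 × 0.75 = 0.1875 and variance 0.25 × 0.75 + 0.75 = 0.9375 each. Their partial correlation is 0.1875/0.9375 = 0.20, so z = 0.20√124/√0.96 = 2.27, and a null mediator path is rejected about 62% of the time. Adding the 12-week step average brings this back to about 5% in simulation.

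**The case against.** A reader might infer that Hypothesis 3 as a whole cannot be answered. The documents do not support that. The hypothesis speaks of the effect without restricting it to steps, Hypothesis 2 just above it covers self-reported activity and quality of life, and the day-84 scores precede the 6- and 12-month measurements of both. The heterogeneity half needs only baseline scores. For these parts the gap is a missing analysis in Section 20, not a fault in measurement timing.

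A reader might also infer that a mediation analysis of steps would usually report mediation wrongly. Under the assumed reverse paths, 70% to 95% of trials would not, and at c = 0.2 the rate is only about 5%. No figure in the documents supports any particular coefficient.

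Nor should 29% be quoted as the power for heterogeneity. It leaves out the baseline-step adjustment that Section 20 already specifies for the primary model.

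Finally, this is the third hypothesis, and neither the sample size nor the primary comparison depends on it. That limits the weight of the point.

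What stands is the core. The most natural reading of the hypothesis includes the step effect, and for that effect no measurement in the schedule can establish temporal order.

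**Conclusion.** The point holds for mediation of the 12-week step average. That conclusion rests on the schedule alone and needs no assumed effect size. The false-mediation range of about 5% to 30% with 128 participants is illustrative: it assumes a 0.5 SD step effect, no true mediation and a reverse path of 0.2 to 0.5. Mediation of later self-reported activity and heterogeneity by baseline score can both be examined but are unplanned. The second has modest power at best for an interaction of 0.25 SD per SD: 37% to 65% with baseline-step adjustment at an assumed correlation of 0.5 to 0.8. The plan should be changed, because a stated mechanism hypothesis invites a causal claim that its step data cannot support.

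**What to change.** 1. In Section 7, state that mediation of the 12-week step average is not testable with the planned measurements and will not be claimed.
2. In Section 20, add an exploratory analysis of day-84 SEE-DK and OEE2-DK as mediators of 6- and 12-month IPAQ and NPAQ. Adjust for the baseline mediator, baseline activity and the 12-week step average. State that the step average is itself a post-randomisation variable, so the question becomes whether the score matters beyond the walking already done, and that unmeasured confounding remains possible.
3. In Section 20, add group × baseline SEE-DK and group × baseline OEE2-DK to the primary step model, labelled exploratory and reported with confidence intervals.

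The cost is a narrower hypothesis, protocol wording and a little more analysis. No new data are needed.

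Optional, if step mediation is to be kept: send SEE-DK and OEE2-DK (9 + 13 = 22 items) through SurveyXact at about week 6. Analyse mean steps over days 43 to 84, adjusted for days 1 to 42. Four of the seven calls fall in weeks 1 to 5, and the adjustment removes early gains, including any part mediated early. This therefore answers only later-period mediation. It adds one short questionnaire and a small participant burden.

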The 42-items questionnaire was developed originally in Danish in 1999 [51] and measures the structural aspect of social relations, with focus on contact frequency and diversity, and functional aspects with focus on perceived social support. CSRQ has been used in several Danish population-based surveys including in the Copenhagen Aging and Midlife Biobank (CAMB) [52]. In a sample of 38-69 old adults the CSRQ showed acceptable face and content validity and good test-retest reliability by 41% of the items had substantial to almost perfect agreement (kappa: 0.65-0.97) and the rest showed moderate agreement (kappa: 0.41-0.60) [53].

The secondary outcomes will also serve as follow up measurements six and 12 months after ending the intervention. They will also be conducted with online surveys.

13. Participant timeline

Time schedule of enrolment, interventions (including any run-ins and washouts), assessments, and visits for participants. A schematic diagram is highly recommended (see Figure).

[figure not shown]

Figure 1. SPIRIT participant timeline.

14. Sample size

Estimated number of participants needed to achieve study objectives is 128 participants. The number will be enough to show a 0.5 standard deviation difference between groups, equal to a moderate effect size. The number of participants will yield a power on 80% with a significance level on 0.05. To account for attrition this study will include 20% more participants than the above mentioned, and hence terminate the inclusion of participants when 154 participants in total and 77 in each group have been enrolled.

15. Recruitment

We will recruit participants through online advertisements on social media and in non-profit organizations working with older adults. We will also try to recruit participants at activity centers and other communities of older adults.

Methods: Assignment of interventions

16. Allocation

16.a. Sequence generation

Participants will be randomly assigned to either the intervention or the control group, with a 1:1 allocation. Eligible participants who have completed the baseline step count, will be randomized in blocks of four participants or more, stratified on sex (M/F) and average baseline step count for the extracted days prior to the allocation. Randomization of participants will happen every week, except weeks with less than four new participants.

16.b Allocation concealment mechanism

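### IPAQ-SF is scored into three levels and, read as written, that ordinal code is analysed as a mean; continuous MET-min/week on a pre-set scale should be named instead

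*Combined protocol and SAP*

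**What the plan says.** Section 12 (Outcomes) lists IPAQ-SF first among the secondary outcomes, measured at baseline, 12 weeks, 6 months and 12 months. Its description says the items "are considered to estimate total physical activity in MET-min/week and time spent sitting". The next sentence gives the only scoring rule: "The score is categorized to three levels of (categories) of PA; low, moderate and high". No cut-points and no expected share per level are given.

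Section 20 (Statistical methods) sets out one model: "The primary outcome will be analyzed as a mixed effects model, where intervention group are analyzed fixed and participants are random effects". Its target is a difference in means: "The analysis will investigate the group difference in average daily step count, adjusted for baseline step count and gender". Then: "Same analysis will be performed on secondary outcomes". No ordinal model, link function or transformation is named for any outcome.

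Section 7 (Objectives) makes self-reported activity part of hypothesis 2: "It is hypothesized that motivational interviewing, will affect self-reported physical activity and quality of life". IPAQ-SF is one of two activity questionnaires that serve it; the other is NPAQ-short.

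**The concern.** Taken together, the scoring rule and the single-model rule send a low/moderate/high code into a model for a mean. Three things follow if that is done.

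- Two participants in the same level count as equally active, however far apart their weekly totals are.
- The model treats low to moderate as the same distance as moderate to high, which nothing in the plan supports.
- The result is a difference in mean category, which cannot be read in any unit of activity.

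The information lost is information the trial already has, since the MET-min/week total comes from the same answers. At stake is part of hypothesis 2: a real effect of the interviews on self-reported activity would be harder to detect and harder to interpret. In addition, copying the step-count model literally adjusts IPAQ-SF for baseline steps and gender but not for baseline IPAQ-SF.

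**Working it through.** **1. The plan's own figure.** Section 14 gives 128 participants for a 0.5 SD difference at 80% power and 0.05 significance, raised by 20% to 154. Sidedness is not stated; two-sided is assumed because it reproduces the number.

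- Normal approximation: n per arm = 2(1.960 + 0.842)² / 0.5² = 62.8, so 63 per arm (126).
- Two-sample t-test: 63.8, so 64 per arm (128), with power 80.1%.
- 128 × 1.2 = 153.6, so 154.

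The stated figures reproduce. Section 14 gives no effect size or SD for IPAQ-SF, so 64 per arm and 0.5 SD serve below only as a yardstick.

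**2. Cost of three levels on a roughly normal scale.** Assumptions: activity is normal with SD 1, mean 0 in control and 0.5 in intervention; control level shares are p1, p2, p3; levels are coded 1, 2, 3; the comparison is an unadjusted t-test on complete data. The shares are assumptions, because the documents give none.

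- Cut-points: c1 = Φ⁻¹(p1), c2 = Φ⁻¹(p1 + p2).
- Intervention shares: Φ(c1 − 0.5), Φ(c2 − 0.5) − Φ(c1 − 0.5), 1 − Φ(c2 − 0.5).
- Standardized effect: d = (m1 − m0) / √((v0 + v1)/2), with m and v the mean and variance of the code in each arm.

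Equal thirds: the intervention shares are 0.176, 0.296, 0.528. Then m0 = 2, v0 = 0.667; m1 = 0.176 + 2(0.296) + 3(0.528) = 2.352; v1 = 0.176 + 4(0.296) + 9(0.528) − 2.352² = 0.580. So d = 0.352 / √0.6235 = 0.445 to rounding. Relative efficiency is (0.445/0.5)² = 0.79.

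Shares 5/25/70: the intervention shares are 0.016, 0.137, 0.847. Then m0 = 2.65, v0 = 0.3275; m1 = 2.831, v1 = 0.172; d = 0.181 / √0.250 = 0.362, and relative efficiency is 0.53 after rounding.

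| Control shares, low/moderate/high (%) | d | Power at 64 per arm | Per arm for 80% |
|---|---|---|---|
| 30/50/20 | 0.452 | 72% | 78 |
| 25/50/25 | 0.450 | 71% | 79 |
| 33/33/33 | 0.445 | 71% | 81 |
| 60/30/10 | 0.437 | 69% | 84 |
| 20/40/40 | 0.437 | 69% | 84 |
| 10/40/50 | 0.417 | 65% | 92 |
| 10/30/60 | 0.395 | 60% | 102 |
| 5/25/70 | 0.362 | 53% | 121 |
| Continuous, normal | 0.500 | 80% | 64 |

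**3. What if MET-min/week is skewed?** The same 0.5 SD shift was placed on the log scale and the totals simulated as log-normal (5,000 trials per setting, 64 per arm).

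| SD of log total | Untransformed total | Log total | Three levels: 33/33/33, 10/40/50, 5/25/70 |
|---|---|---|---|
| 0.5 | 75% | 80% | 70%, 65%, 53% |
| 0.8 | 68% | 80% | 69%, 65%, 54% |
| 1.0 | 60% | 80% | 70%, 65%, 52% |
| 1.3 | 51% | 80% | 70%, 64%, 54% |

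At a log SD of 1.3 the categories do at least as well as the raw total for all three sets of shares. The advantage therefore belongs to the transformed total, not to any continuous total. The simulated totals contain no zeros, so the 80% does not cover a lump of participants who report no activity.

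**The case against.** **The category may not be the analysed variable.** Section 12 describes an instrument and mentions three quantities: the MET-min/week total, sitting time and the levels. It never says which is the endpoint, and a model for a mean fits the continuous total more naturally. This stands as a limit: that the category enters the model is an inference, and a reader who concludes that the plan certainly discards the total goes beyond the text. But categorizing is the only thing Section 12 does to the score. For other scales the same section says how the score is formed (a 0-60 sum for UCLA, a 0-90 total for SEE-DK, 1-5 averages for OEE2-DK). If the total was meant, the plan leaves three candidates open, and the same sentence would settle it.

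**A reader might infer that most real changes in activity would count as no change.** The documents do not support this. The planned model computes no IPAQ-SF change score. The share of intervention participants who stay in one level also depends on the level shares, the size of the shift and the correlation between baseline and endpoint. Over shifts of 0.25 to 1.0 SD, correlations of 0.3 to 1.0 and three sets of shares, it runs from 39% to 90%. What can be said is that differences within a level are not seen.

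**A reader might also infer that power is lost whatever the comparator.** Step 3 shows otherwise for untransformed, strongly skewed totals.

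**The outcome is minor.** The primary outcome is device-measured steps, hypothesis 2 also draws on NPAQ-short and EQ-5D-5L, and Section 12 itself reports a pooled correlation of only 0.30 between IPAQ-SF and accelerometry. This stands, and it limits the weight of the point without removing the mismatch of scale and model.

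**Conclusion.** The point holds in a conditional form. Read as written, Sections 12 and 20 put a three-level ordinal code into a mean-difference model, and no other statement in the plan names the IPAQ-SF variable to be analysed. If the category is analysed, the loss of within-level differences, the forced equal spacing and the missing activity unit follow directly. The power figures (about 53% to 72% against about 80%) rest on assumed level shares, a 0.5 SD shift borrowed from the generic sample-size statement, 64 complete cases per arm, and a comparator that is roughly normal or made so by transformation. The point is worth correcting before the data are analysed, but it touches one secondary outcome under hypothesis 2. The step-count analysis and the 128 and 154 participants are unaffected.

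**What to change.** In Sections 12 and 20:

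- Name continuous total MET-min/week as the analysed IPAQ-SF outcome.
- Fix its scale now, with one transformation that handles zeros, for example log(x+1) or ranks. Making the transformation depend on how the residuals look would leave the choice until after the data are seen.
- Adjust the comparison for baseline IPAQ-SF MET-min/week on the same scale.
- Report low/moderate/high descriptively, or with a proportional-odds model labelled as supporting.

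The cost is a few sentences of protocol text. It needs no new data and no extra participants, since the total and its baseline are already collected. The small downside is that an effect on a log or rank scale is less direct to interpret than a difference in MET-min/week.
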